9.2 Handling of Missing Data

Handling of missing data for the efficacy analyses is described below.

9.2.1 Categorical Endpoints

Non-Responder Imputation (NRI): The NRI approach will categorize any subject who has a missing value at a specific visit as a non-responder for that visit. The only exception will be if the subject is a responder both before and after a specific visit window, then the subject will be categorized as a responder for the visit. The NRI will be the primary approach in the analysis of categorical variables.

Of note, during the Primary Analysis for Period A upon completion of Week 16, the NRI approach will only be performed at all visits up to Week 16.

9.2.2 Continuous Endpoints

Mixed-Effect Model Repeat Measurement (MMRM) will be the primary and only approach to handle missing data for continuous endpoints among all ITT Populations. The MMRM will be conducted using mixed model including observed measurements at all visits, using all available data even if a subject has missing data at some (but not all) post-baseline visits during the analysis period. An unstructured variance covariance matrix (UN) will be used. If the model cannot converge, an appropriate covariance structure matrix (e.g., autoregressive (1) or compound symmetry) will be used. The parameter estimations are based on the method of restrictive maximum likelihood (REML). The fixed effects will be used to report model-based means at corresponding visits.

Of note, during the Primary Analysis for Period A upon completion of Week 16, the MMRM analysis will only be performed at all visits up to Week 16.

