APPENDIX D. ACTIVITY SCHEDULE

The following table shows the required activities across the Screening and subsequent study visits. The individual activities are described in detail in the **Operations Manual**. Allowed modifications due to COVID-19 and/or the geo-political conflict in Ukraine and surrounding impacted regions are detailed within the Operations Manual.

The follow-up phone call is not required for any subject who initiates commercial risankizumab.

Study Activities Table

Activity	Screening	Baseline	Week 4	Week 16	Week 28	Week 40	Week 52 / Premature Discontinuation	Follow-Up Call 20 Weeks after Last Dose
	Day -30 to Day -1	Day 1	Day 29	Day 113	Day 197	Day 281	Day 365	Day 421
Visit Window			± 3 Days		± 7 Days			
INTERVIEWS & QUESTIONNAIRES								
Informed consent	✓							
Demographics	✓							
Eligibility criteria	✓	✓						
Medical (including psoriasis)/surgical history	✓	✓						
Drug, tobacco (including e-cigarettes), and alcohol history	✓							
Adverse event assessment	✓	✓	✓	✓	✓	✓	✓	✓
Prior/concomitant therapy	✓	✓	✓	✓	✓	✓	✓	✓
Dispense handheld ePRO device	✓							
Collect handheld ePRO device				✓				
Patient Reported Outcomes Study-G: GPSS, GenPs-SFQ, PatGA-Genital, DLQI, and HADS Study-S: PSS, Scalp Itch NRS, DLQI, and HADS * GPSS and PSS collected DAILY from Screening to Week 16 and then at site visits. GenPs-SFQ collected WEEKLY from Screening to Week 16 and then at site visits. All other PROs collected at site visits from Baseline to Week 52.	✓*	✓*	✓*	✓*	✓*	✓*	✓*	
Latent TB risk assessment form	✓							

Activity	Screening	Baseline	Week 4	Week 16	Week 28	Week 40	Week 52 / Premature Discontinuation	Follow-Up Call 20 Weeks after Last Dose
	Day -30 to Day -1	Day 1	Day 29	Day 113	Day 197	Day 281	Day 365	Day 421
Visit Window			± 3 Days		± 7 Days			
LOCAL LABS & EXAMS								
12-lead ECG	✓							
Height (screening only) and weight	✓						✓	
Vital signs	✓	✓	✓	✓	✓	✓	✓	
Physical examination (targeted physical exam possible at any time, if required)	✓	✓					✓	
Efficacy assessments Study-G: sPGA-G, sPGA Study-S: scalp IGA, PSSI, sPGA	✓	✓	✓	✓	✓	✓	✓	
BSA	✓	✓						
Urine pregnancy test (for females of childbearing potential only, performed prior to dosing)		✓	✓	✓	✓	✓		
Optional photography (not performed at Premature Discontinuation Visit)		✓	✓	✓	✓	✓	✓	
CENTRAL LABS								
HIV/HBV/HCV screening	✓							
Follicle-stimulating hormone (FSH) (if applicable, per operations manual)	✓							

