3.2 Secondary Endpoints

Ranked secondary endpoints are:

Study-G

1. Achievement of sPGA-G of 0 at Week 16, among subjects in the ITT_G population.
2. Achievement of DLQI of 0 or 1 at Week 16, among subjects in the ITT_G population.
3. Achievement of clinically meaningful (≥ 4 -point) improvement from baseline on the Genital Psoriasis Itch NRS at Week 16 among subjects with a baseline score ≥ 4 , among subjects in the ITT_G population.
4. Achievement of GenPs-SFQ item 2 score of 0 or 1 at Week 16 among subjects with a baseline score ≥ 2 , among subjects in the ITT_G population.

Study-S

1. Achievement of $\geq 90\%$ improvement from baseline in PSSI (PSSI 90) at Week 16, among subjects in the ITT_S population.

2. Achievement of PSSI 75 response at Week 16, among subjects in the ITT S population.
3. Change from baseline in PSS at Week 16, among subjects in the ITT S population.
4. Achievement of PSSI 100 response at Week 16, among subjects in the ITT S population.
5. Achievement of PSS of 0 at Week 16, among subjects in the ITT S population.

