11.1.4 Psoriasis Symptoms Scale (PSS)

The PSS is a 4-item PRO instrument that assesses the severity of psoriasis symptoms in patients with moderate to severe psoriasis, using a recall period of 1 day. The symptoms include pain, redness, itching and burning from psoriasis. Current symptom severity is assessed using a 5-point Likert-type scale ranging from 0 (none) to 4 (very severe). Until Week 16, the weekly average score is calculated based on the 7 available daily scores from the days within each visit window that were closest to the nominal. If values from 4 or more days of the 7 day period are missing, then the rolling weekly average for that particular 7 day period will be set to missing.

The PSS was developed based on published evidence supporting the development of two similar, proprietary PRO instruments: the Psoriasis Symptom Inventory and the Psoriasis Symptom Diary.

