13.0 Overall Type-I Error Control

For Study-G and Study-S, overall type-I error will be controlled under a two-sided significance level of 0.05 respectively for each study by testing the primary endpoint,

followed by the ranked secondary endpoints, in a hierarchical order as described in Section 3.1 and Section 3.2.

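### As the SAP reads, the Period A mixed model for PSS change has only Weeks 4 and 16, so diary data from the weeks between cannot inform a missing Week 16 value

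*SAP*

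**What the plan says.** - **Endpoint.** SAP 3.2 ranks "Change from baseline in PSS at Week 16" third in Study-S. Under SAP 13.0, "overall type-I error will be controlled under a two-sided significance level of 0.05" by testing in fixed order, so this test stands before PSSI 100 and PSS 0.
- **Collection.** Protocol Appendix D has "GPSS and PSS collected DAILY from Screening to Week 16 and then at site visits".
- **Visit value.** In SAP 11.1.4, "the weekly average score is calculated based on the 7 available daily scores from the days within each visit window", taking the days nearest the nominal day. "If values from 4 or more days of the 7 day period are missing", the average is missing. The SAP does not define the windows.
- **Model.** SAP 9.2.2 fits the MMRM "using mixed model including observed measurements at all visits". In the Week 16 analysis, "the MMRM analysis will only be performed at all visits up to Week 16". Appendix D schedules two post-baseline visits in that span, Week 4 and Week 16.
- **Missing data.** In SAP 9.2.2 the MMRM "will be the primary and only approach to handle missing data for continuous endpoints". SAP 9.4.3 rules out sensitivity analyses for ranked secondary endpoints, whereas SAP 9.3.3 gives the primary endpoints both multiple imputation and a tipping-point analysis.
- **Follow-up.** Protocol 5.6 keeps subjects who stop study drug on the visit schedule unless they withdraw consent.

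**The concern.** An MMRM handles a missing Week 16 value by conditioning on what it has been given. Here that is baseline, the stratification factors and, if available, Week 4. The next time point is 12 weeks later. Missing at random given Week 4 is a stronger assumption than missing at random given the weeks just before the subject was lost, and the diary that could relax it is already collected.

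Suppose subjects leave because their symptoms worsen after Week 4, and this happens more often on placebo. The model then predicts their Week 16 score too favourably, and the treatment difference shrinks. A subject with neither a usable Week 4 mean nor a Week 16 mean contributes no post-baseline information at all, whatever the diary holds. The Week 16 mean can also be missing for a subject still in the study, through the rule on missing diary days.

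At stake is the size of the estimate for a ranked endpoint, with no planned analysis that would show how far it depends on this assumption.

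**Working it through.** **1. The plan's own figure.** No power, SD or effect is stated for PSS. The nearest figure is the Study-S primary endpoint (SAP 2.4): 11% against 11 + 37 = 48%, 50 per arm, two-sided 0.05. With a pooled chi-square test, z = [0.37√50 − 1.96√(2 × 0.295 × 0.705)] / √(0.48 × 0.52 + 0.11 × 0.89) = (2.616 − 1.264) / 0.589 = 2.29. Power is 98.9%, consistent with the stated figure of more than 90%.

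**2. What is left out.** Weeks 5 to 15 are 16 − 4 − 1 = 11 weeks. Weeks 1 to 3 are unused as well, so 14 of 16 weekly means stay outside the model.

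**3. Bias, by simulation (all inputs assumed).** There were 150,000 subjects per arm, so that sampling noise is negligible. Weekly PSS had variance 1, a random intercept and weekly autocorrelation 0.85 or 0.95. Dropout fell in Weeks 5 to 15, with a logit hazard rising by 1 or 2 per SD of that week's PSS. Placebo dropout was set near 5, 10 or 20%; dropout on risankizumab followed from the same rule. Week 16 was estimated by sequential regression for monotone missingness, standing in for the likelihood fit.

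Bias toward the null in SD units, true effect 0.8 SD:

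| Placebo dropout | Weeks 4, 16 | Weeks 4, 8, 12, 16 | All 16 weeks |
|---|---|---|---|
| about 5% | 0.007–0.018 | 0.003–0.009 | ≤ 0.001 |
| about 10% | 0.013–0.035 | 0.006–0.018 | ≤ 0.001 |
| about 20% | 0.026–0.061 | 0.012–0.032 | ≤ 0.001 |

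Adding Weeks 8 and 12 removes about half. In the worst case the bias falls from 0.061 to 0.032, so 0.029/0.061 = 48% is removed. With no true effect and the same mechanism in both arms, the bias was at most 0.003 SD, which is simulation noise.

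**4. Against the precision.** SE = SD × √(2/50) = 0.2 × SD, or 0.14 to 0.20 for an adjusted SD of 0.7 to 1.0. With SD 0.9, SE is 0.18. Power at 0.8 is Φ(0.80/0.18 − 1.96) = 99.4%. With a bias of 0.05 it is Φ(0.75/0.18 − 1.96) = 98.6%.

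**5. A harsher set.** Assume a true difference of −4.2 and SD 3.5 (1.2 SD), correlations with Week 16 of 0.55 (Week 4) and 0.82 (Week 12), and missingness driven by Week 15 symptoms. At 8, 14 and 21% missing on placebo:
- Weeks 4 and 16 gave −3.98, −3.89 and −3.77, which is 5, 7 and 10% too small.
- Adding Weeks 8 and 12 gave −4.11, −4.08 and −4.01. The share of bias removed is 0.13/0.22, 0.19/0.31 and 0.24/0.43, or 56 to 61%.
- With 25% missing in each arm, SE = 3.5√(2/37.5) = 0.81. Even −3.77 then gives power Φ(3.77/0.81 − 1.96), about 99.6%.

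**6. Precision of the larger model.** In 2,000 simulated trials per scenario with 50 per arm and the same difference and SD, the empirical SE was 0.66 to 0.71 for both models. An unstructured matrix has k(k + 1)/2 parameters: 3 for two time points, 10 for four, 136 for sixteen.

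**The case against.** The best defence is that this is a design choice, not an error. SAP 3.3 evaluates endpoints at scheduled visits, and a visit-based MMRM follows from that. If Week 16 is observed, leaving out Weeks 5 to 15 does not bias the Week 16 contrast, and Protocol 5.6 is written to keep Week 16 observed. This stands: the problem is conditional.

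A reader might go further than the documents allow in four ways.

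- **That late dropout does bias this endpoint.** The documents give no dropout rate or reason. Bias needs Week 16 to be missing for reasons beyond baseline and Week 4.
- **That a subject lost in Week 13 is necessarily predicted from baseline and Week 4 alone.** Choosing the days nearest the nominal day matters only if a window holds more than seven days. With undefined windows, a wide Week 16 window could take in such a subject's last diary days. The Premature Discontinuation visit also records PSS, and the SAP does not say which time point that record belongs to. Even the reading that the model holds only Weeks 4 and 16 is inferred from the schedule, though it is the plain reading.
- **That type I error is at risk because the endpoint is in the hierarchy.** The calculation shows none when both arms share the dropout mechanism. Arm-specific mechanisms were not simulated and could act in either direction.
- **That Weeks 8 and 12 remove the bias entirely.** This appears only if missingness is made to depend on Week 12 itself, which builds in the answer.

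**Conclusion.** This is a cheap improvement, not a flaw that threatens the conclusion. As written, the Period A model for PSS change has two post-baseline time points and ignores most of a daily diary, and no sensitivity analysis tests what that implies. If Week 16 PSS is lost for reasons related to symptoms after Week 4, the difference is understated by about 0.01 to 0.06 SD at 5 to 20% placebo dropout and an assumed 0.8 SD effect. The harsher set, with a 1.2 SD effect, gives more, up to about 10% of the effect. In both, the bias runs against risankizumab and power barely moves.

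These sizes rest on assumed dropout, SD, correlation and effect. A smaller true PSS effect would leave less spare power. The structural part (which time points enter, undefined windows, no sensitivity analysis) rests on the documents alone.

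**What to change.** In SAP 9.2.2 and 11.1.4:

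1. Name the Period A time points for the PSS model as Weeks 4, 8, 12 and 16, with Weeks 8 and 12 taken from the diary weekly means.
2. Define a 7-day window for each, so that earlier diary days are not carried into the Week 16 value. State which time point, if any, a Premature Discontinuation record belongs to.
3. Keep the unstructured covariance and the Week 16 contrast as the test. The estimand and the place in the hierarchy do not change.
4. Apply the same time points to GPSS change in Study-G. That endpoint is not alpha-controlled, so this is for consistency.

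The cost is the window definitions, two more derived records per subject and a 4×4 covariance matrix (10 parameters, about 100 subjects). No new data or visits are needed. Defining the Week 16 window also settles the value used for PSS 0, the fifth ranked endpoint. The change to the main model should be made before the Week 16 unblinding; after that, the four-point model can only be supplementary. An alternative is to leave the model alone and use the diary means as auxiliary variables in a multiple-imputation sensitivity analysis.

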9.3 Primary Efficacy Endpoints and Analyses

9.3.1 Primary Efficacy Endpoints

The primary endpoints are:

- Study-G: Achievement of sPGA-G of 0 or 1 at Week 16, among subjects in the ITT G population.
- Study-S: Achievement of scalp IGA of 0 or 1 at Week 16, among subjects in the ITT S population.

9.3.2 Analysis of Primary Efficacy Endpoints

The attributes of the estimand corresponding to the primary efficacy objective are summarized in [Table 1](#).

Table 1. Summary of the Estimand Attributes Corresponding to the Primary Efficacy Objective(s)

Estimand Label	Attributes of the Estimand				
	Treatment	Endpoint	Population	Handling of Intercurrent Events	Statistical Summary
Study-G: sPGA-G 0/1 at Week 16	RZB and placebo	Study-G: Achievement of sPGA-G of 0 or 1 at Week 16	Adult subjects with moderate to severe genital psoriasis	No intercurrent event is considered	Difference in the proportion of subjects achieving sPGA-G of 0 or 1 at Week 16, regardless of premature discontinuation of study drug, in the RZB group compared with the placebo group
Study-S: scalp IGA 0/1 at Week 16		Study-S: Achievement of scalp IGA of 0 or 1 at Week 16	Adult subjects with moderate to severe scalp psoriasis	No intercurrent event is considered	Difference in the proportion of subjects achieving scalp IGA of 0 or 1 at Week 16, regardless of premature discontinuation of study drug, in the RZB group in compared with the placebo group

9.3.3 Sensitivity and Supplementary Analyses of the Primary Efficacy Endpoints

A sensitivity analysis for the primary endpoint, using MI to handle missing data:

To assess the robustness of the primary analysis, a CMH analysis with missing data handled by MI will be conducted on the primary endpoints sPGA-G 0/1 at Week 16 in the ITT G Population for Study-G and scalp IGA 0/1 at Week 16 in the ITT S Population for Study-S. Markov Chain Monte Carlo (MCMC) will be first applied to augment continuous variables (which are dichotomized to derive the primary endpoints) into monotonic missing pattern and PROC MI will be used to generate 30 datasets using the regression method. The variables to be included in the imputation model for each study are: treatment group, actual value of stratification factors (weight and number of prior biologic therapies for psoriasis), Baseline value, and measurements at each visit in

Period A. The random seeds for MCMC and the random seeds for PROC MI are specified in [Appendix D](#). The imputed post-baseline measurements will be rounded to the same precision as the observed data before the determination of responder status. Subjects will be characterized as responders or non-responders based on MI imputed datasets. Using the Cochran-Mantel-Haenszel (CMH) model adjusted by actual value of stratification factors (weight and number of prior biologic therapies for psoriasis), the imputed endpoints will be analyzed using each of the 30 datasets. SAS PROC MIANALYZE will be used to generate the final inferences of the response rate difference between RZB group and placebo.

Tipping Point Analysis, a sensitivity analysis for the primary endpoints: To assess the robustness of the primary analysis, a tipping point analysis will be conducted on the primary endpoints sPGA-G 0/1 at Week 16 in the ITT G Population for Study-G and scalp IGA 0/1 at Week 16 in the ITT S Population for Study-S.

Details of the tipping point analysis are described below using proportion of subjects achieving sPGA-G 0/1 at Week 16 among ITT G Population for RZB vs. placebo as an example.

M1	Total number of subjects with missing sPGA-G 0/1 status at Week 16 among ITT G Population in the placebo group
M2	Total number of subjects with missing sPGA-G 0/1 status at Week 16 among ITT G Population in the RZB group
X1	Number of subjects who are imputed as responders, among the M1 subjects with missing sPGA-G 0/1 status at Week 16 among ITT G Population in the placebo group. $X1 = 0, \dots, M1$
X2	Number of subjects who are imputed as responders among the M2 subjects with missing sPGA-G 0/1 status at Week 16 among ITT G Population in the RZB group. $X1 = 0, \dots, M2$

- For each pair of $(X1, X2)$, simulations will be used to randomly draw $X1$ subjects from the $M1$ subjects with missing values in placebo group and $X2$ subjects from the $M2$ subjects with missing values in RZB group. These randomly selected $X1$ subjects in placebo and $X2$ subjects in RZB group with missing sPGA-G 0/1 status at Week 16 will be imputed as responders. The remaining subjects missing

sPGA-G 0/1 status at Week 16 will be imputed as non-responders. Analysis of RZB vs. placebo will be conducted using the combined observed data and imputed data for each treatment group. A p-value will be calculated using the CMH test adjusted by actual value of stratification factors.

2. The simulation will be repeated 50 times for each pair of (X1, X2) and the median p-value will be used for the conclusion. The random seed for simulation will be preset as specified in [Appendix D](#). If one pair of parameters is found to just reverse the study conclusion (i.e., median p-value > 0.05 [tipping point analysis will be performed only if the primary analysis reached p-value ≤ 0.05]), then these parameters will be the tipping points.
3. Of note, an extreme case analysis will be checked first, where all missing data in placebo are imputed as responders and all missing data in the RZB group are imputed as non-responders. If the extreme case analysis does not reverse the conclusion based on the NRI approach, complete tipping point analysis will not be performed.

Similar tipping point analysis procedure as that for the sPGA-G 0/1 at Week 16 will be conducted on scalp IGA 0/1 at Week 16 among ITT S Population for RZB vs. placebo.

9.4 Secondary Efficacy Endpoints and Analyses

9.4.1 Ranked Secondary Efficacy Endpoints

The ranked secondary endpoints are as defined in Section [3.2](#).

9.4.2 Analyses of Ranked Secondary Efficacy Endpoints

The attributes of the estimands corresponding to the ranked secondary efficacy objectives are summarized in [Table 2](#).

Table 2. Summary of the Estimand Attributes Corresponding to the Ranked Secondary Efficacy Objectives

Estimand Label	Attributes of the Estimand				
	Treatment	Endpoint	Population	Handling of Intercurrent Events	Statistical Summary
Study-G					
sPGA-G 0/1 at Week 16	RZB and placebo	Achievement of sPGA-G of 0 or 1 at Week 16	adult subjects with moderate to severe genital psoriasis	No intercurrent event is considered	The difference in the proportion of subjects achieving each endpoint, regardless of premature discontinuation of study drug, in the RZB group versus the placebo group
DLQI 0/1 at Week 16		Achievement of DLQI of 0 or 1 at Week 16			
Genital Psoriasis Itch NRS improvement ≥ 4 at Week 16		Achievement of clinically meaningful (≥ 4 -point) improvement from baseline on the Genital Psoriasis Itch NRS at Week 16 among subjects with a baseline score ≥ 4			
GenPs-SFQ item 2 score of 0/1 at Week 16		Achievement of GenPs-SFQ item 2 score of 0 or 1 at Week 16 among subjects with a baseline score ≥ 2			

Estimand Label	Attributes of the Estimand				
	Treatment	Endpoint	Population	Handling of Intercurrent Events	Statistical Summary
Study-S					
PSSI 90 response at Week 16	RZB and placebo	Achievement of $\geq 90\%$ improvement from baseline in PSSI response at Week 16	Adult subjects with moderate to severe scalp psoriasis	No intercurrent event is considered.	Difference in the proportion of subjects achieving each endpoint, regardless of premature discontinuation of study drug, in the RZB group versus the placebo group
PSSI 75 response at Week 16		Achievement of PSSI 75 ($\geq 75\%$ improvement from baseline in PSSI) response at Week 16			
PSSI 100 response at Week 16		Achievement of PSSI 100 (100% improvement from baseline in PSSI) response at Week 16			
PSS of 0 at Week 16		Achievement of PSS of 0 at Week 16			
PSS change from Baseline at Week 16	RZB and placebo	Change from baseline in PSS at Week 16	Adult subjects with moderate to severe scalp psoriasis	No intercurrent event is considered.	Difference in mean change from Baseline in PSS at Week 16, regardless of premature discontinuation of study drug, in the RZB group versus the placebo group

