3.3 Secondary Endpoint

Ranked Secondary Endpoints

Study-G

1. Achievement of sPGA-G of 0 at Week 16
2. Achievement of DLQI of 0 or 1 at Week 16
3. Achievement of clinically meaningful (≥ 4 -point) improvement from baseline on the Genital Psoriasis Itch NRS at Week 16 among subjects with a baseline score ≥ 4
4. Achievement of GenPs-SFQ item 2 score of 0 or 1 at Week 16 among subjects with a baseline score ≥ 2

Study-S

1. Achievement of $\geq 90\%$ improvement from baseline in PSSI 90 at Week 16
2. Achievement of PSSI 75 ($\geq 75\%$ improvement from baseline in PSSI) response at Week 16
3. Change from baseline in PSS at Week 16
4. Achievement of PSSI 100 (100% improvement from baseline in PSSI) response at Week 16
5. Achievement of PSS of 0 at Week 16

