2.0 Study Objectives and Design

2.1 Study Objectives

Primary Objective

The primary objective of the study is to evaluate the efficacy and safety of risankizumab (RZB) for the treatment of moderate to severe genital psoriasis (Study-G) or moderate to severe scalp psoriasis (Study-S) in adults who are candidates for systemic therapy.

Primary Efficacy Endpoints

The primary efficacy endpoints are achievement of sPGA-G of 0 or 1 at Week 16 for subjects in Study-G, and achievement of scalp IGA of 0 or 1 at Week 16 for subjects in Study-S.

The hypotheses corresponding to the primary efficacy endpoints are:

- The proportion of subjects achieving sPGA-G of 0 or 1 in adult subjects with moderate to severe genital psoriasis at Week 16 in subjects randomized to RZB is greater than those randomized to placebo in Study-G.
- The proportion of subjects achieving scalp IGA of 0 or 1 in adult subjects with moderate to severe scalp psoriasis at Week 16 in subjects randomized to RZB is greater than those randomized to placebo in Study-S.

The estimands corresponding to the primary endpoints in Study-G and Study-S are defined as follows:

- Study-G: Difference in the proportion of subjects achieving sPGA-G of 0 or 1 in adult subjects with moderate to severe genital psoriasis at Week 16, regardless of premature discontinuation of study drug, in the RZB group compared with the placebo group.
- Study-S: Difference in the proportion of subjects achieving scalp IGA of 0 or 1 in adult subjects with moderate to severe scalp psoriasis at Week 16, regardless of premature discontinuation of study drug, in the RZB group compared with the placebo group.

Intercurrent events handling: No intercurrent event is considered.

Ranked Secondary Endpoints

The list of ranked secondary endpoints can be found in Section [3.2](#).

The hypotheses corresponding to the secondary endpoints are:

- Binary endpoints: The proportion of subjects achieving each endpoint in subjects treated with risankizumab is greater than those treated with placebo, in Study-G or Study-S.

- Continuous endpoint (change from Baseline in PSS for Study-S): The mean reduction from Baseline in PSS at Week 16 in subjects treated with risankizumab is greater than those treated with placebo in Study-S.

The estimands corresponding to the ranked secondary efficacy endpoints are:

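### Does the sPGA-G 0/1 row in SAP Table 2 change the first ranked secondary endpoint of Study-G?

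*SAP*

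**What the plan says.** SAP 3.2 opens the Study-G ranked list with "Achievement of sPGA-G of 0 at Week 16, among subjects in the ITT_G population". Protocol 3.3 has the same first item, "Achievement of sPGA-G of 0 at Week 16", and so does the protocol synopsis.

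SAP 9.4.2 then gives a table titled "Summary of the Estimand Attributes Corresponding to the Ranked Secondary Efficacy Objectives". Its first Study-G row is labelled as sPGA-G 0/1, and its endpoint cell reads "Achievement of sPGA-G of 0 or 1 at Week 16". Table 1 in SAP 9.3.2 already carries that endpoint as the primary: "Study-G: Achievement of sPGA-G of 0 or 1 at Week 16". No row of Table 2 covers sPGA-G 0.

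Three places in the SAP say where the ranked endpoints are defined, and each points to Section 3.2:

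- SAP 2.1: "The list of ranked secondary endpoints can be found in Section" 3.2.
- SAP 9.4.1, directly above Table 2: "The ranked secondary endpoints are as defined in Section" 3.2.
- SAP 13.0, on type I error: the primary is tested first, "followed by the ranked secondary endpoints, in a hierarchical order as described in Section 3.1 and Section 3.2".

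**The concern.** The row gives the wrong responder threshold for an endpoint inside the alpha-controlled sequence, in the section headed as the analysis of those endpoints. The threshold is wrong in two cells and in two wordings (0/1 in the label, 0 or 1 in the endpoint), so it is not an artefact of text extraction. Neither the SAP version history nor SAP 14.1 declares a change to this endpoint.

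The worry is what happens if a programmer builds the Study-G sequence from Table 2. The first ranked step would then repeat the primary test and pass whenever the primary passed. Complete clearance would leave the controlled sequence. DLQI, itch and GenPs-SFQ item 2 would no longer wait on it. Clear skin is a harder target than clear or minimal, so success on the primary does not imply success on sPGA-G 0, and the lost gate would be a real one.

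**Working it through.** **The plan's own figure.** The only design figure for Study-G is the power for the primary endpoint (Protocol 7.8, SAP 2.4): placebo 13%, difference 53 points, hence 66% on risankizumab, 50 per arm, two-sided 0.05, more than 90% power. With the usual normal approximation,

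power = Φ[(d√n − 1.96·√(2p̄q̄)) / √(p₁q₁ + p₂q₂)]

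- d√n = 0.53 × √50 = 3.748
- p̄ = (0.66 + 0.13)/2 = 0.395, so 1.96 × √(2 × 0.395 × 0.605) = 1.355
- √(0.66 × 0.34 + 0.13 × 0.87) = √0.3375 = 0.581
- power = Φ(2.393/0.581) = Φ(4.12) = 0.99998

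The stated figure is reproduced. It concerns sPGA-G 0/1 only and does not depend on Table 2.

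**Row-by-row comparison of SAP 3.2 with Table 2.**

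| Study | Rank in SAP 3.2 | Endpoint | Row in Table 2 | Endpoint agrees? |
|---|---|---|---|---|
| G | 1 | sPGA-G 0 | none (row 1 shows sPGA-G 0/1) | no |
| G | 2 | DLQI 0/1 | 2 | yes |
| G | 3 | Genital itch NRS, 4-point improvement | 3 | yes |
| G | 4 | GenPs-SFQ item 2, 0/1 | 4 | yes |
| S | 1 | PSSI 90 | 1 | yes |
| S | 2 | PSSI 75 | 2 | yes |
| S | 3 | Change in PSS | 5 | yes |
| S | 4 | PSSI 100 | 3 | yes |
| S | 5 | PSS 0 | 4 | yes |

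Matching endpoints: 3 + 5 = 8 of 9. Three of the five Study-S rows are out of rank order and no row is numbered, so Table 2 cannot serve as a testing sequence. It groups endpoints by type.

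**Does sPGA-G 0 lack anything it needs?**

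- *Definition and rank:* SAP 3.2, Protocol 3.3 and the synopsis, all in agreement.
- *Estimand:* SAP 2.1 and Protocol 3.1 give one estimand for every binary ranked endpoint, a difference in response proportions that counts subjects whether or not they stopped study drug early. The treatment, population, intercurrent-event and summary cells of Table 2 are common to the Study-G rows.
- *Test:* SAP 9.1 applies the stratified CMH method to categorical variables in general.
- *Missing data:* SAP 9.2.1 makes NRI the primary approach for categorical variables in general.
- *Reporting:* SAP 3.3 and Protocol 3.4 have every primary and secondary variable evaluated at the scheduled visits.

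Nothing is missing.

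**If Table 2 were programmed literally.** The sequence would be primary, primary again, DLQI, itch, SFQ, each at two-sided 0.05.

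- The repeated step has the same p-value as the primary and cannot fail once the primary has passed.
- It remains a fixed sequence set in advance, so familywise error stays at 0.05 in Study-G.
- Three distinct secondaries rather than four would remain under control.

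How often the missing gate would matter depends on sPGA-G 0 rates, which the documents do not give. As an assumption only, take placebo at 2% to 13% and risankizumab at 30% to 66%. The upper ends are the planning rates for 0/1, which the rate of 0 cannot exceed. With 50 per arm, power for sPGA-G 0 is:

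| Assumed placebo | Risankizumab 30% | 40% | 50% |
|---|---|---|---|
| 2% | 0.978 | 0.999 | 1.000 |
| 5% | 0.921 | 0.993 | 1.000 |
| 10% | 0.712 | 0.946 | 0.996 |
| 13% | 0.544 | 0.876 | 0.986 |

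At 60% and 66% power is at least 0.9996 throughout. The gate would therefore stop the sequence with a probability between about 0 and 1 − 0.544 = 0.456. The high end needs every planned placebo responder to be completely clear. This range applies only under the misreading.

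**The case for a change.** The strongest case for acting is that the row is simply wrong. Section 9.4.2 is a natural place for a programmer or an outside reader to look, and a controlled endpoint should not be misstated there. The slip remains in version 4.0. Version 3.0 corrected another sPGA-G threshold, the baseline subgroup, so the sponsor has treated comparable slips as worth an update. The repair would take two cells. Saying that Section 3.2 governs limits the harm but does not make the row right.

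All of that stands as a description of the text. What does not stand is the step to a consequence for the trial. To go wrong, an analyst would have to pass over the cross-reference directly above the table, ignore the section that sets the testing order, and accept as a secondary endpoint the one that Table 1 lists as primary. The subgroup correction differs in kind: there the SAP replaced a definition that the analysis would have used. Here the definition the analysis uses is already correct.

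**Conclusion.** This is a clerical slip in a summary table, and no change to the plan follows. It affects one of nine ranked secondary rows (one of four in Study-G). Followed as written, the plan tests sPGA-G 0 immediately after the primary, with the right estimand, test and missing-data rule. Correcting the row would change no p-value, estimate, sample size or testing order. Familywise error is 0.05 per study under either reading.

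The conclusion rests on one assumption: that the analysis follows SAP 3.2, as SAP 2.1, 9.4.1 and 13.0 direct. Nothing in either document suggests that Table 2 drives the testing. If it did, the loss would be one controlled claim and one gate in Study-G. sPGA-G 0 would still be reported as an efficacy variable, so a reader could see its result.
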